7.3 INDEX PROCEDURE

Thrombectomy using the ClotTriever System is considered the index procedure and the treatment phase of the study. The procedure is conducted under fluoroscopic/angiographic guidance. Refer to the Instructions for Use (IFU) for techniques and methods for device deployment.

Anticoagulation therapy to ensure an activated clotting time of 250 – 300 seconds is recommended.

Subjects who require conversion to open surgery due to treatment failure with the device will be followed for safety through 30 days, or until any treatment related adverse events resolve, which ever is later.

The following data are to be recorded on the subject's Procedure CRF.

- Length of procedure (from ClotTriever sheath access to last removal of sheath)
- Number of ClotTriever passes
- Number of ClotTriever devices used, with lot numbers
- Largest sheath size used
- Pre- and post-procedure venogram findings
- Pre- and post-procedure IVUS measurements
- Concurrent use of balloon angioplasty and/or stenting and/or placement of IVC Filter
- Adjunctive therapy (thrombolysis and/or additional thrombectomy).
- Anticoagulant used and amount

Venogram runs/cines must be, and IVUS runs should be, acquired pre-ClotTriever and post-ClotTriever^d. If adjunctive therapy is used, a third venogram and IVUS run post-therapy will be acquired. All procedural venograms cines and IVUS images will be de-identified, labeled appropriately, uploaded and sent to the Core Laboratory.

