10.5 Missing Data

Every effort will be made to minimize the amount of missing data. Recognizing the difficulty of avoiding some missing data, however, data imputation methods with sensitivity imputation analyses will be specified in the Statistical Analysis Plan. Subjects with missing effectiveness data will be assumed to have missing data at random and will be imputed by random selection with replacement of data from subjects with pre- and post-intervention measurement of thrombus removal. The robustness of the multiple imputation outcome will be tested with a tipping point analysis encompassing all possible imputation outcomes.

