3.2. Primary Analysis Population

The Primary Analysis dataset is a subset of subjects with unilateral acute or subacute DVT of less than or equal to a 6-week duration, without recent (≤ 3 months) venous intervention. The first 91 subjects enrolled who meet these criteria will complete the Primary Analysis dataset. Enrollment of this type of subject will continue once the Primary Analysis cohort is fully accrued, i.e., past the 91 subjects needed for the primary endpoint analyses. These additional subjects will be included in the Full Analysis dataset.

4. Incomplete Date Handling and Missing Data

Incomplete dates will follow the following imputation assignment rules:

1. If day is missing but month and year are present, the day will be set to the first date of the month.
2. If both day and month are missing but year is present, then January 1st will be used as the imputed value.
3. If year is missing, then the date is considered missing. In general, missing data points are not imputed.

Subjects with missing effectiveness data will be assumed to have data missing at random and will be imputed by random selection with replacement of data from subjects with pre- and post-intervention measurement of thrombus removal. By repeating this process, e.g. for 5,000 separate data replicates, an empirical distribution of primary effectiveness endpoint can be derived for an estimated 95% confidence interval based on the quantiles of the empirical distribution. The robustness of the multiple imputation outcome will be tested with a tipping point analysis encompassing all possible imputation outcomes.

5. Statistical Methods and Analysis

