5.1. Sample Size

The performance goal of 34% has been established for the primary safety endpoint, based on a one-sided 97.5% exact binomial test. The 30-day MAE rate is anticipated to be approximately 20%. Under this assumption, the required sample size to achieve a level of 82% power is 86 subjects (**Table 1**).

Assuming 5% attrition over 30 days, enrollment of 91 subjects is necessary for the Primary Analytic Dataset.

Table 1. Sample Size - Primary Safety Endpoint

Measure	
Performance goal	34%
Anticipated freedom from MAE	20%
Significance level	.025
Statistical test	One-sided exact binomial test
Desired power level	82%
Required sample size prior to 5% 30-day attrition rate	86
Required sample size after attrition adjustment	91

A performance goal of 30% has been established for the primary effectiveness endpoint. Anticipating an actual Technical Success rate of approximately 50%, and based upon a one-sided 97.5% exact binomial test, the required sample size to achieve a level of 97% power is 85 subjects (**Table 2**). Since the primary effectiveness endpoint is determined at the time of the index procedure, no attrition has been considered for lost to follow-up or other censoring events. However, the effectiveness endpoint is evaluated in the Primary Analytic Effectiveness cohort, and it is assumed that 3% of enrolled subjects will be treated for DVT in the absence of core laboratory-assessed visible thrombus in the TVS. Assuming a 3% attrition rate for subjects without thrombus, enrollment of 88 subjects will be necessary.

Table 2. Sample Size - Primary Effectiveness Endpoint

Measure	
Performance goal	30%
Anticipated technical success rate	50%
Significance level	.025
Statistical test	One-sided exact binomial test
Desired power level	97%
Required sample size prior to 3% attrition for subjects without thrombus	85
Required sample size after attrition adjustment	88

The required sample size is greater for the primary safety endpoint; 91 vs. 88 subjects. Thus, a total of 91 subjects will be enrolled in the Primary Analysis dataset; providing approximately 91 subjects in the Primary Safety cohort and 88 subjects in the Primary Effectiveness cohort for the primary safety and effectiveness analyses, respectively. The overall power of the study is 80%.

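### Missing post-device venograms are imputed by an unconditional draw that ignores adjunctive therapy and the post-adjunctive venogram; if those images are lost mainly in subjects who go on to adjunctive therapy, Technical Success is overestimated

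*SAP*

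**What the plan says.** Technical Success is a Marder score reduction of at least 75% from the baseline venogram to the venogram taken after the device but before any adjunctive thrombus removal (Protocol 5.2, SAP 2.2).

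When that reading is missing, SAP section 4 assumes the data are missing at random, and the value "will be imputed by random selection with replacement of data from subjects with pre- and post-intervention measurement of thrombus removal". Protocol 10.5 has the same rule: "imputed by random selection with replacement of data from subjects with pre- and post-intervention measurement of thrombus removal". Neither text restricts donors by any covariate, and neither scores any missing subject as a failure. Both add a tipping-point analysis over every possible set of imputed outcomes. The success criterion in Protocol 10.4 does not refer to it.

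Protocol 7.3 puts adjunctive therapy (thrombolysis or additional thrombectomy) on the Procedure CRF and also states: "If adjunctive therapy is used, a third venogram and IVUS run post-therapy will be acquired".

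On sample size, SAP 5.1 makes no allowance for missing images: "no attrition has been considered for lost to follow-up or other censoring events".

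**The concern.** A draw from one undivided pool gives every missing subject the observed average chance of success. That is right only if missingness is unrelated to outcome (missing completely at random). Missing at random is a weaker assumption, but using it means conditioning on the observed variables that predict both missingness and outcome. The plan collects an obvious candidate and does not use it.

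The scored image must fall between the last ClotTriever pass and any adjunctive therapy. An operator who sees residual thrombus could go straight to adjunctive treatment and leave that image out. The imputation would then replace likely failures with average subjects. A subject still below 75% reduction after further thrombus removal could be imputed as a success. At stake are an upward bias in the primary effectiveness estimate and a higher chance of passing a 30% goal that has not been exceeded.

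**Working it through.** **Inputs from the documents (SAP 5.1).**
- Performance goal: 30%.
- Expected Technical Success: 50%.
- Test: exact binomial, one-sided, alpha 0.025.
- Stated size and power: "the required sample size to achieve a level of 97% power is 85 subjects".
- Inflation: 3% of subjects expected to have no visible thrombus, which takes 85 to 88.

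**The plan's own figures.** The cut-off is the smallest r with P(X ≥ r | n, 0.30) ≤ 0.025.
- n = 85: r = 35, exact alpha 1.85%, power at 50% = 95.9% (97% stated).
- 85 / (1 − 0.03) = 87.6, rounded up to 88, as stated.
- n = 88: r = 36 (40.9%), exact alpha 1.9%, power 96.5%.

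**Assumed inputs (not in the documents).** Let a be the share receiving adjunctive therapy, m the share of those with no interim venogram, and s the true device-only success rate among adjunctive users. All missingness is placed in adjunctive users, and the overall true rate is 30%.

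**Bias.** With q = a × m, the success rate among observed subjects is (0.30 − q·s) / (1 − q). An unconditional draw reproduces this rate on average, so it is also the expected estimate. Example: a = 20%, m = 25%, s = 5% gives q = 0.05 and (0.30 − 0.0025) / 0.95 = 31.3%.

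**Chance of passing.** Let M be the number missing, binomial(88, q). Let x be the observed successes, binomial(88 − M) at the rate above. The imputed successes are binomial(M, x / (88 − M)). The trial passes if observed plus imputed successes reach 36. Summing over M and x:

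| a | m | s | Expected missing | Estimate | Pass |
|---|---|---|---|---|---|
| – | 0 | – | 0 | 30.0% | 1.9% |
| 10% | 10% | 15% | 0.9 | 30.2% | 2.2% |
| 10% | 10% | 5% | 0.9 | 30.3% | 2.3% |
| 20% | 10% | 15% | 1.8 | 30.3% | 2.5% |
| 20% | 10% | 5% | 1.8 | 30.5% | 2.7% |
| 20% | 25% | 15% | 4.4 | 30.8% | 3.5% |
| 20% | 25% | 5% | 4.4 | 31.3% | 4.4% |
| 30% | 1/3 | 15% | 8.8 | 31.7% | 5.9% |
| 30% | 1/3 | 5% | 8.8 | 32.8% | 8.7% |

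**Separating bias from noise.** If missingness is unrelated to outcome (s = 30% in the same formula), the estimate is 30.0%. The pass probability is then 2.4% with 4.4 missing and 3.0% with 8.8. That part of the excess is noise from testing a single draw. The rest is bias.

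**Worst case.** If a fixed number are missing and all are true failures, the pass probability is 2.4% (1 missing), 3.0% (2), 5.4% (5) and 10.8% (9).

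**Conditioned draws (simulation).** Drawing donors within adjunctive-use strata returns an estimate of 30.0%, with pass probabilities of 2.1–2.2% in the 4.4- and 8.8-missing scenarios at s = 5%. The next check scores post-adjunctive failures as failures, with a = 30% and m = 1/3, and assumes that half of the adjunctive users who fail with the device also fail on the post-adjunctive venogram. If the donor pool still contains such subjects, the estimate is 29.8%, 29.3% and 29.1% at s = 5%, 15% and 25%. Removing them from the donors restores about 30.0% in each case.

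**The case against.** **Selective loss is an inference.** No passage says the interim image tends to be lost when clot remains. The venogram is marked as required, post-ClotTriever runs must be acquired (Protocol 7.3), and required venograms go to the Core Laboratory (Protocol 13.5). This largely stands. A reader might infer that the estimate is biased upward and type I error exceeds 2.5% as the plan is written. The documents do not support that: with about one image missing the error stays below 2.5%, and it reaches 2.5% only at about two. Against this, departures from the assessment schedule are not recorded as deviations (Protocol 7.1 and 11.3), so some loss is possible and would trigger no deviation report.

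**The later venogram does not measure the device-only result.** A reader might call a subject below 75% after adjunctive therapy a known device failure. Protocol 7.5 recognises that thrombus can form in the treated segment during the index procedure, so failure is almost certain, not certain. Adjunctive use alone shows less still, because no passage ties it to the 75% threshold.

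**The arithmetic is not the SAP's procedure.** The SAP describes a quantile interval from, for example, 5,000 replicates. The figures above test one draw against the exact cut-off. They show the effect of the donor rule and should not be read as that interval's error rates.

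**The tipping-point analysis includes the all-failures outcome.** It would show whether success depends on the draw. But no decision rule is attached to it, so the primary result would stand whatever it showed.

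**Conclusion.** The point holds conditionally. The donor rule is unconditional, is valid only if missingness is unrelated to outcome, and ignores two relevant items that the study collects. If interim venograms are lost mainly in adjunctive-therapy subjects with a below-average device-only success rate, the primary estimate is biased upward. Under the assumed rates the bias is 0.2–0.5 percentage points with about 1–2 images missing and 1.7–2.8 points with about 9. The corresponding pass probabilities run from 2.2% to 8.7%, against 1.9% with complete data. If almost no images are missing, the effect is negligible. The change is worth making because the direction of bias is plausible, the endpoint is primary and the remedy is cheap.

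**What to change.** Amend SAP section 4, and Protocol 10.5 to match:

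1. Score as failure any subject with no post-device venogram whose post-adjunctive venogram shows less than 75% Marder reduction from baseline.
2. For the remaining missing subjects, draw donors only from subjects with the same adjunctive-therapy status. Among adjunctive users, exclude donors whose own post-adjunctive venogram shows less than 75% reduction, so that donors match recipients.
3. State a fallback for an empty or very small donor stratum, such as scoring as failure. Do not split further by clot age unless numbers allow.
4. Keep the tipping-point analysis.

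This needs SAP and protocol wording and a few lines of code, using data already collected. The price is slightly more imputation noise and possibly a slightly less favourable estimate. Power is not a barrier: with 5, 9 or 13 missing subjects who are all true failures and are all scored as such, power at an overall true rate of 50% is 96.9%, 97.3% and 97.6%.

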10.4 STUDY SUCCESS CRITERIA

The study will be considered a success if both primary endpoints meet their respective performance goals. For the safety endpoint, this translates into observing a one-sided 97.5% lower confidence limit (LCL) of the point estimate below 34% and for the effectiveness endpoint, it means observing a one-sided 97.5% LCL above 30%.

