10.8 SAMPLE SIZE

The performance goal of 34% has been established for the primary safety endpoint, based on a one-sided 97.5% exact binomial test. The 30-day MAE rate is anticipated to be approximately 20%. Under this assumption, the required sample size to achieve a level of 82% power is 86 subjects (**Table 2**). Assuming 5% attrition over 30 days, enrollment of 91 subjects is necessary for the Primary Analytic Dataset.

Table 2. Sample Size - Primary Safety Endpoint

| Measure | |
|------------------------------|-------------------------------|
| Performance goal | 34% |
| Anticipated freedom from MAE | 20% |
| Significance level | .025 |
| Statistical test | One-sided exact binomial test |
| Desired power level | 82% |

| Required sample size prior to 5% 30-day attrition rate | 86 |
|--|----|
| Required sample size after attrition adjustment | 91 |

A performance goal of 30% has been established for the primary effectiveness endpoint. Anticipating an actual Technical Success rate of approximately 50%, and based upon a one-sided 97.5% exact binominal test, the required sample size to achieve a level of 97% power is 85 subjects (**Table 3**). Since the primary effectiveness endpoint is determined at the time of the index procedure, no attrition has been considered for lost to follow-up or other censoring events. However, the effectiveness endpoint is evaluated in the Primary Analytic Effectiveness cohort, and it is assumed that 3% of enrolled subjects will be treated for DVT in the absence of core laboratory-assessed visible thrombus in the TVS. Assuming a 3% attrition rate for subjects without thrombus, enrollment of 88 subjects will be necessary.

Table 3. Sample Size - Primary Effectiveness Endpoint

| Measure | |
|--|-------------------------------|
| Performance goal | 30% |
| Anticipated technical success rate | 50% |
| Significance level | .025 |
| Statistical test | One-sided exact binomial test |
| Desired power level | 97% |
| Required sample size prior to 3% attrition for subjects without thrombus | 85 |
| Required sample size after attrition adjustment | 88 |

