5.3. Primary Safety Endpoint Analysis

The primary safety endpoint for this study will be assessed in the Primary Analysis Safety cohort and is a composite endpoint of any MAE within 30 days, as determined by the independent Medical Monitor. The MAE rate is defined as the 30-day rate of all-cause mortality, major bleeding, new symptomatic PE documented by CTPA, or rethrombosis of the target venous segment(s). The MAE rate will be compared to a performance goal with the following null and alternative hypotheses:

$$H_0: P_S \geq PG_S \text{ versus } H_A: P_S < PG_S$$

where P_S is the proportion of subjects with MAE through 30 days and PG_S is the safety performance goal derived from the studies reporting the elements contained in the composite MAE endpoint.

The exact binomial one-sided 97.5% confidence interval will be used to test the primary safety endpoint.

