5.4. Primary Effectiveness Endpoint Analysis

The primary effectiveness endpoint is Technical Success, defined by complete or near complete thrombus removal. Thrombus removal is determined by the Marder score at the index procedure, measured after use of the study device but prior to the use of adjunctive devices. Effectiveness will be assessed in the Primary Analysis Effectiveness Cohort^a and will be compared to a performance goal with the following null and alternative hypotheses:

$$H_0: P_E \leq PG_E \text{ versus } H_A: P_E > PG_E$$

where P_E is the proportion of subjects with Technical Success, defined as complete or near complete removal of thrombus with the study device, measured by a venographically-determined reduction of $\geq 75\%$ in the Marder score in the TVSs. The effectiveness performance goal, PG_E , is Technical Success defined in the same manner, derived from published literature.

^a This dataset was designed to exclude those subjects treated who underwent venous thrombectomy for lesions that were non-thrombotic in nature. For instance, those with non-thrombotic May-Thurner lesions that have external compression or scar but who do not have demonstrable intraluminal thrombus. These subjects will remain in the Primary Safety Cohort and will be assessed for safety endpoints but will not be assessed for the effectiveness endpoints.

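### If any effectiveness data are missing, the 95% interval in SAP section 4 leaves out sampling error and covers the true Technical Success rate far less than 95% of the time

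*SAP*

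**What the plan says.** SAP section 4 (Incomplete Date Handling and Missing Data) assumes that missing effectiveness data are missing at random. Protocol 10.5 has the same rule: such subjects "will be imputed by random selection with replacement of data from subjects with pre- and post-intervention measurement of thrombus removal". SAP section 4 then repeats this process, for example 5,000 times, so that "an empirical distribution of primary effectiveness endpoint can be derived for an estimated 95% confidence interval based on the quantiles of the empirical distribution". It adds: "The robustness of the multiple imputation outcome will be tested with a tipping point analysis encompassing all possible imputation outcomes".

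The success rule is in Protocol 10.4: "for the effectiveness endpoint, it means observing a one-sided 97.5% LCL above 30" percent. The only effectiveness test named is in the sample size sections. Protocol 10.8 has: "Anticipating an actual Technical Success rate of approximately 50%, and based upon a one-sided 97.5% exact binominal test". SAP 5.1 agrees: "based upon a one-sided 97.5% exact binomial test, the required sample size to achieve a level of 97% power is 85 subjects".

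For safety, SAP 5.3 names the analysis method: "The exact binomial one-sided 97.5% confidence interval will be used to test the primary safety endpoint". For effectiveness, SAP 5.4 says only that the result "will be compared to a performance goal with the following null and alternative hypotheses". It names no interval and does not refer to section 4.

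**The concern.** The repeated process is the imputation. No sentence resamples the observed subjects or adds binomial variance, so the observed results are the same in all 5,000 replicates. The spread of the replicates then shows only how much the few imputed values could vary. The interval narrows as the data become more complete and would have zero width with complete data, which is the wrong behaviour for a confidence interval on a proportion.

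There are two consequences:

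- A figure labelled a 95% confidence interval would be reported for a co-primary endpoint with a small fraction of its stated coverage.
- The success decision is not fully defined when data are missing. Protocol 10.4 needs one lower limit, imputation gives many completed datasets with different exact limits, and no rule combines them.

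If an analyst used the only effectiveness interval that the SAP describes as the limit in Protocol 10.4, type I error on this endpoint would also rise sharply.

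**Working it through.** **Inputs.** Effectiveness cohort 88, goal 30%, anticipated rate 50%, one-sided 0.025 exact test, 85 subjects before the 3% adjustment (Protocol 10.8, SAP 5.1). The number missing, m, is not in the documents. I assume m = 3 and show 1 to 10.

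**The plan's own figure.** With 85 subjects the exact test needs 35 successes: P(X ≥ 35) is 0.0185 at 30% and 0.959 at 50%. The stated power is 97%, so it reproduces to within about a point. Enrolment is 85/0.97 = 87.6, rounded up to 88, as stated.

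**The SAP interval.** Let n = 88 − m and let x be the observed successes. Given x, the imputed successes follow Binomial(m, x/n). With many replicates the interval tends to

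(x + q)/88, with q the 2.5% and 97.5% quantiles of Binomial(m, x/n).

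With m = 3 its width cannot exceed 3/88 = 3.4 points. At a true 50% the imputation SD is √(3 × 0.25)/88 = 1.0 point, while the binomial standard error is √(0.25/88) = 5.3 points.

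| Observed | SAP section 4 interval | Exact 95% interval, observed subjects |
|---|---|---|
| 27/85 | 30.7%–34.1% | 22.1%–42.8% |
| 42/85 | 47.7%–51.1% | 38.4%–60.5% |

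**Coverage.** Sum the Binomial(n, p) probabilities over every x whose interval contains p. With m = 3 these are x = 25–26 at 30%, 33–35 at 40% and 41–44 at 50%.

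| Missing of 88 | True 30% | True 40% | True 50% |
|---|---|---|---|
| 1 | 9.3% | 8.7% | 17.0% |
| 3 | 18.7% | 26.0% | 33.5% |
| 5 | 28.0% | 34.4% | 33.9% |
| 10 | 46.3% | 51.0% | 57.2% |

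An endpoint exactly equal to p counts as covering. That favours the SAP: with open endpoints the 33.5% becomes 17.2%. A simulation with 5,000 replicates per dataset gave 20%, 26% and 32% at m = 3. The exact interval on the 85 observed subjects covers 96.8%, 96.5% and 97.1%.

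**If the exact test decides.** A completed dataset needs 36/88 (lower limit 30.5%; 35/88 gives 29.5%). With m = 3, the share of replicates that pass is P(Binomial(3, x/85) ≥ 36 − x):

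- x = 33: 5.9%
- x = 34: 35.2%
- x = 35: 79.6%

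For these counts the verdict depends on a combining rule that the documents do not give. The chance that x falls in 33–35 is 4.1%, 26.0% and 4.9% at a true 30%, 40% and 50%. The tipping-point analysis does not settle it. At 35/85, the exact limits with 0, 1, 2 and 3 imputed successes are 29.5%, 30.5%, 31.6% and 32.7%, which straddle the goal, and SAP section 4 does not say how scenarios are judged.

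**If the SAP quantile were the lower limit.** With m = 3, 27/85 passes, since 27/88 = 30.7%. Type I error is P(X ≥ 27 | 85, 0.30) = 40%. Over m = 1 to 10 it ranges from 24% to 46%. With m = 3, this rule and the exact test on observed subjects would disagree with probability 38% at a true 30% and 4% at 50%.

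**The case against.** The strongest reply is that this interval need not decide anything. The exact binomial test is the only effectiveness test named, so the 40% error rate belongs to a reading with less support. That stands: the type I figures are conditional and should not set the severity. The reported interval is still invalid, and the deciding limit is still unspecified once values are imputed.

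A second reply is that few data will be missing. Protocol 7.3 requires venograms before and after the device, Protocol 13.5 requires that they be sent, and the endpoint is measured at the index procedure. Also, cohort entry needs core-laboratory thrombus at baseline, so a subject without a baseline venogram probably leaves the cohort and is not imputed. This narrows the route mainly to a missing or unreadable post-device run, or a baseline run that cannot be scored. It does not close it. Protocol 7.1 calls the schedule recommended, and Protocol 11.3 does not record departures in procedures or data points as deviations. Coverage is poor at every count from 1 to 10.

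A third reply is that a bootstrap was meant, since the talk of data replicates and an empirical distribution suggests one. It may have been, but a programmer following the text would not resample the observed subjects.

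Finally, applying the exact test to each tipping-point scenario is a natural choice. It is not written down, and it would still leave open what to conclude when scenarios disagree.

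**Conclusion.** The concern holds. As written, the SAP section 4 interval omits sampling error. With 3 of 88 missing it covers a true 30%, 40% or 50% in 19%, 26% or 34% of trials; over 1 to 10 missing the range is 9% to 57%. On the better-supported reading, in which the exact test decides, the damage is an invalid interval on a co-primary endpoint, plus an undefined success limit when the observed count is near the threshold (a 5% chance at the planned 50%, 26% at a true 40%). Inflated type I error follows only on the less supported reading. With no missing data the step is not triggered.

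The mechanism and the under-coverage are firm. The exact size rests on the assumed number missing and on a cohort of 88. This should be fixed before analysis.

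**What to change.** In SAP section 4, replace the interval with one that carries sampling variance: in each of the 5,000 replicates, resample all subjects, then impute the missing ones within that resample. At 27/85 this gives 21.6%–42.0%. With 3 missing, its coverage is 95.6%, 95.3% and 97.1% at 30%, 40% and 50%.

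In SAP 5.4, name one deciding limit against 30%:

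- **Rule (a):** the lower 2.5% quantile of the resample-then-impute distribution, or the exact binomial limit when nothing is missing. This keeps the imputation in Protocol 10.5 and needs a sentence reconciling it with the exact test in Protocol 10.8 and SAP 5.1.
- **Rule (b):** the one-sided 97.5% exact binomial lower limit in observed subjects. This keeps the named test and needs Protocol 10.5 and SAP section 4 amended so that imputation is supportive.

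The cutoffs are identical for 1 to 9 missing (at 10 they are 33 and 32), so stating a rule matters more than which one is chosen. With 3 missing both need 35/85, with one-sided error 1.9% and power 95.9%; with all 88 observed the exact test has 96.5%. State also that each tipping-point scenario is judged by the exact limit.

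The cost is a few lines of text and code, a wider reported interval, and the reconciling sentence or protocol amendment. No subjects are added.
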